# 8 Study population

## 8.1 Inclusion and exclusion criteria

### *Inclusion criteria:*

- Patients with a confirmed venous malformation of the upper/lower extremity independent of previous therapy with epi- and/or subfascial localization of the venous malformation independent of the local extent (cross-articular or not)
- Compression stocking can be put on independently or by the parents
- Written declaration of consent present

### *Exclusion criteria:*

- Lack of compliance, patient is not available for control appointments
- Additional drug therapy (anticoagulation) for extensive venous malformations with threatening thromboembolic complications
- Known allergic reaction/intolerance to components of flat-knitted compression stockings
- Pregnancy
- Rejection of the study participation by the patient
- Contraindications for the planned MRI examination (pacemakers, implants not suitable for MRI, claustrophobia)

- Occurrence of an emergency situation
- Severe heart failure as contraindication for compression therapy
- PAD as contraindication for compression therapy

## 8.2 Participant number

Approximately 25 patients with venous malformation of the upper/lower extremities, age 6-70 years are to be included. Compression in the form of individually fitted compression stockings will be applied by the patient himself or by his parents.

## 8.3 Recruitment routes and measures

Patients are informed about the possibility of participating in the study during a routine presentation of the vascular surgery consultation hours. If patients are willing to participate, they will be fully informed about objectives and methods, benefits and risks, and the revocability of their participation in the study.

# 9 Study plan

## 9.1 Procedure for informing about and obtaining consent

Participants can only be included in the study after a written declaration of consent has been given. The written declaration of consent requires that the patients are informed orally and in written form about the objectives and methods, benefits and risks as well as the revocability of their participation in the study.

It must be clearly communicated to the study participant that a withdrawal of consent is possible at any time and without any disadvantage for further treatments or therapy.

The original of the consent form is kept in the study folder at the study site. The participant receives a copy of the patient information and consent form.

## 9.2 Measurements

### *Investigation day 0*

After informing of the subjects, gender, age and localization of the venous malformation are recorded for all study participants as basic data. The measurements for the individualized preparation of class I and II compression stockings are then taken.

Between investigation day 0 and 28 participants do not wear any compression stockings.

### ***Investigation day 28***

Participants fill out the SF-12 questionnaire. Then a measurement of the volume of the affected extremity is performed by perometry and MRI. First without any compression stocking and afterwards with both individualized compression stockings of class I and II.

This is followed by a four-week treatment with one of the two compression stockings, whereby the selection of compression class will be double-blinded.

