## 6 Target parameters

### 6.1 Primary target:

- Volume of affected extremity(ml)
  - *This target is measured non-invasively by perometry and MRI*

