### 6.2 Secondary targets:

- Volume of affected extremity immediately after application of compression (ml)
  - *This target is measured non-invasively by perometry and MRI*
- Quality of life by SF-12 (short form 12) questionnaire
- Handling and wearing comfort of compression stockings in everyday life by questionnaire "*Tragekomfortbogen*" (comfort of wearing questionnaire)

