### 9.3 Recording of target parameters

- Determination of volume of the malformation by perometry
- Determination of volume of the malformation by MRI
- Determination of quality of life by SF-12 (questionnaire)
- Determination of handling and wearing comfort of compression stockings in everyday life by "*Tragekomfortbogen*" (*comfort of wearing*) (questionnaire)

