## **11 Biometrics**

Continuous variables are given as means with standard deviation. Categorial variables are given as frequencies and percentage. Although making use of a crossover design, we do not expect any carryover or period effects due to the nature of the treatments. Therefore, differences between the treatments and baseline measurements are evaluated using Wilcoxon signed rank tests. Moreover, linear regression analysis is used to adjust for variations in

baseline measurements for the direct comparison of compression classes. A p-value below or equal to 0.05 is considered to indicate statistical significance.

All results will be calculated using R version 3.5.1 (R Foundation for Statistical Computing, Vienna, Austria).

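### Perometry compares a bare limb with a stockinged limb and no fabric correction is stated, so a true reduction of a few percent could be understated, masked or reversed

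*Combined protocol and SAP*

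**What the plan says.** Section 6.1 makes the volume of the affected extremity, in ml, the primary target and adds: "This target is measured non-invasively by perometry and MRI". The two instruments are not ranked.

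Under Investigation day 28, section 9.2 says: "Then a measurement of the volume of the affected extremity is performed by perometry and MRI". The order of conditions follows: "First without any compression stocking and afterwards with both individualized compression stockings of class I and II". For days 56 and 84 the text lists questionnaires only. Figure 1, which shows the measurement schedule, is not reproduced in the copy reviewed.

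Section 11 gives the analysis: "differences between the treatments and baseline measurements are evaluated using Wilcoxon signed rank tests". It adds a linear regression that adjusts the direct comparison of the two classes for baseline.

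The visible text does not describe how the perometer works, how the stocking is handled in a stocking-on reading, how the limb is outlined on MRI, or how thick the fabric is.

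**The concern.** In the text, the only volume contrast with baseline sets an uncovered limb against a covered one. A device that reads the outer contour would count the fabric as limb, and only in the treated conditions. That is a shift in one direction, not noise. It does not average out over patients, and the baseline adjustment in section 11 cannot remove a volume that is absent at baseline.

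The primary hypothesis, that class I already has a volume-relevant effect, rests on this contrast. If the true reduction is of the same order as the fabric volume, perometry could show no change, or an increase, when the limb has in fact become smaller. The shift is proportionally larger in thin limbs. The trial admits arms and legs at ages 6-70 (section 8.2), so it would also differ between patients.

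**Working it through.** The plan gives no expected volume change, SD or power, so it has no figure of its own to reproduce.

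**Inputs from the documents.** Bare and stocking-on measurement on day 28 (section 9.2); Wilcoxon signed rank test of treatment against baseline, significance at p ≤ 0.05 (section 11); about 25 patients (section 8.2).

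**Assumed inputs.** Perometry records the outer contour; the limb is a cylinder of circumference C and length L; the fabric has uniform thickness t = 0.5-1.5 mm and covers the whole measured segment; the test is two-sided.

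**Step 1: added volume.** Limb volume is V = C²L/(4π). Fabric of thickness t raises it by the fraction (1 + 2πt/C)² − 1, which is close to 4πt/C.

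| C | t = 0.5 mm | t = 1 mm | t = 1.5 mm |
|---|---|---|---|
| 40 cm | 1.6% | 3.2% | 4.8% |
| 26 cm | 2.4% | 4.9% | 7.4% |

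In ml, with t = 1 mm:
- C = 40 cm, L = 70 cm: V = 1600 × 70/(4π) = 8,913 ml; 2πt/C = 0.0157; 1.0157² − 1 = 3.2%, or 282 ml.
- C = 26 cm, L = 45 cm: V = 676 × 45/(4π) = 2,421 ml; 2πt/C = 0.0242; 1.0242² − 1 = 4.9%, or 118 ml.

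Partial coverage scales these down. If half the measured segment is covered, 3.2% becomes 1.6%.

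**Step 2: break-even thickness.** Measured change = true change + fabric volume. A true 3% reduction is cancelled, to a close approximation, when (1 + 2πt/C)² = 1.03, so t = C(√1.03 − 1)/(2π). This gives 40 × 0.01489/6.283 = 0.095 cm, or 0.95 mm, at C = 40 cm, and 26 × 0.01489/6.283 = 0.062 cm, or 0.62 mm, at C = 26 cm. Both lie inside the assumed range.

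**Step 3: effect on the planned test.** Wilcoxon signed rank test, n = 25, 4,000 simulated trials per case, normal paired differences, assumed SD of change 3%, fabric volume taken as the same percentage in every patient:

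| True reduction | Fabric volume | Significant decrease | Significant increase |
|---|---|---|---|
| 3% | 0% | 99.5% | 0.0% |
| 3% | 1.5% | 63.3% | 0.0% |
| 3% | 3% | 2.4% | 2.3% |
| 3% | 5% | 0.0% | 88.3% |
| 5% | 3% | 87.5% | 0.0% |
| 5% | 5% | 2.2% | 2.5% |
| 5% | 6% | 0.0% | 34.6% |

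The result depends on how fabric volume compares with true effect. When fabric volume is well below the true reduction, the effect is understated but often still found. When the two are equal, it is lost. When fabric volume is larger, the sign changes.

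**Step 4: class I against class II.** Both conditions carry fabric, so the added volumes cancel if the fabrics are equally thick.

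**The case against.** The strongest reply is that the key premise is not in the documents. They name perometry but do not say what surface it records or how a stocking-on reading is processed. Section 11 is one general sentence that mentions neither perometry nor raw values, so silence about a correction does not prove that none is intended. Thickness, limb size, coverage, true effect and SD are likewise assumed. All of this stands, and it limits the point to a conditional one. What remains is that the text prescribes bare and covered readings, tests treatment against baseline, and contains no step that would take the fabric out.

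A reader might infer more than the documents support:

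- **That the whole primary outcome is biased.** MRI measures the same target in the same session and need not include fabric if the limb is outlined at the skin. The plan does not say how MRI is outlined or which instrument decides, so MRI limits the problem without settling it.
- **That a reduction of a few percent would be masked.** It could be. In step 3, a 3% reduction is still found in 63.3% of trials at 1.5% fabric volume, and a 5% reduction in 87.5% at 3%.
- **That the comparison between classes is biased too.** This needs fabrics of different thickness, and nothing in the documents suggests a difference.
- **That only a method showing the skin can solve it.** Subtracting a measured fabric volume would also work.
- **That a false benefit could result.** Under the stated assumption the error only enlarges the stocking-on volume, so it cannot create a reduction against baseline.

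**Conclusion.** The point holds in conditional form. If perometry reads the outer contour, the planned comparison with baseline adds the stocking's volume to the treated conditions only. Under full coverage and a thickness of 0.5-1.5 mm this is about 1.6-4.8% at 40 cm and 2.4-7.4% at 26 cm, and proportionally less with partial coverage. The direction follows from the outer-contour assumption alone; the size depends on the other assumed figures.

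The consequence is a possible understatement, loss or reversal of a true reduction in the perometric result for each class against baseline. A null or positive perometric difference could therefore not be interpreted without knowing the fabric volume. The point should be settled before analysis, because the plan has no rule for the case where perometry and MRI disagree.

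**What to change.** In sections 9.2 and 11, state how the stocking is handled. Either of two routes would do:

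1. Subtract each stocking's fabric volume from the stocking-on perometry value. Obtain it as measured thickness times covered limb surface, or from a perometry run of the stocking on a rigid form.
2. Base the comparison with baseline on MRI volume outlined at the skin, in the bare and stocking-on conditions alike, where the MRI covers the same segment as perometry.

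Name the chosen measure as the one that decides the comparison with baseline, and report uncorrected perometry as secondary only. If perometry as performed here already excludes the fabric, a sentence in section 9.2 saying so, and how, would close the point.

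The cost is one thickness or form measurement per stocking, or extra contouring of images already planned, plus a small calculation and the added wording. The MRI route depends on image coverage, which the plan does not state and which should be checked first.

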### ***Investigation day 56***

After four weeks of compression therapy with the first compression stocking all subjects are examined at day 56 by SF-12 questionnaire and by the questionnaire "Tragekomfortbogen" (*comfort of wearing questionnaire*). Then the therapy is continued for four more weeks with the remaining compression stocking that has not yet been worn. Even during this compression therapy the compression class is unknown to the patient and investigator.

### ***Investigation day 84***

After the four weeks lasting therapy with the other compression class, participants are examined at day 84 in the two questionnaires (SF-12 and "Tragekomfortbogen" [*comfort of wearing questionnaire*]) again.

Figure 1 shows the graphical presentation of the planned measurements as well as their chronological sequence for each subject.

[figure not shown]

Figure 1: graphical presentation of all measurements with chronological sequence for each subject

### 9.3 Recording of target parameters

- Determination of volume of the malformation by perometry
- Determination of volume of the malformation by MRI
- Determination of quality of life by SF-12 (questionnaire)
- Determination of handling and wearing comfort of compression stockings in everyday life by "*Tragekomfortbogen*" (*comfort of wearing*) (questionnaire)

### 9.4 Total study duration

Corresponding to the number of patients, the expected total duration of the study until the inclusion of the last patient is approximately 12 months. Participation in the study overall takes approximately 4,5 hours per patient. For the investigation day 0 we assume an examination duration of approximately three hours. Each of the following investigation days (day 28, 56 and 84) will last approximately half an hour. There are four examination time points per patient needed.

## 10 Risk-benefit analysis

### 10.1 All study related risks

#### *Time periods without compression therapy*

While patients do not wear stockings (especially between investigation day 0 and 28), swelling and slight pain of the affected extremity may occur. However, there are no health risks.

#### *Compression therapy*

Incorrect measured compression stockings can cause skin damage, which can result in lacerations, blisters and pressure sores or necrosis. Nerve damage or deep vein thrombosis can also develop. Since the stockings are individually fitted by experts and only low compression classes are used, the risk of such damage is considered extremely low. Other risks associated with compression therapy will be avoided by exclusion of patients with contraindications for compression therapy.

#### *MRI*

Since it is a native MRI (1.5 or 3.0 Tesla) without contrast medium, hardly any risks are to be expected from the examination.

Damage caused by metal-containing implants etc. is avoided by excluding these patients from the examination.

Claustrophobia may occur, in which case the examination is aborted.

The noise exposure caused by the examination can lead to reduced hearing ability, therefore all patients wear hearing protection. Due to the relatively short duration of the examination of 20 minutes and the wearing of hearing protection, the risk of damage to the inner ear is considered extremely low.

The native MRI examination with field strengths of 1.5 or 3.0 Tesla is a routine routine method and no negative changes in the organism have been described so far.

### ***Perometry***

There are no known risks or side effects related to perometry.

## **10.2 Benefits associated with the study**

The data obtained in the study can provide essential information about the behavior of venous malformations under compression therapy and the quality of life during this therapy. It is therefore possible that this therapeutic procedure can be used in the future to treat patients conservatively with an increased quality of life.

## **10.3 Termination criteria**

### ***Termination criteria for the individual participant:***

Participation in the study is discontinued if any study related risks e.g. skin or nerve damage/deep vein thrombosis caused by compression stockings or contraindications for MRI occur.

### ***Termination criteria for the whole study:***

Termination of the entire study must be declared if significant and unobserved serious adverse health effects, which have not been known or observed so far, occur. Otherwise, a termination of the entire study is not planned.

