## **10.4 Statement on medical justifiability**

Based on previous experience with compression therapy and MRI the risk of occurrence of unwanted events is stratified as extremely low.

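### The written whole-study termination rule covers only previously unknown harms, so no number of the serious stocking harms named in section 10.1 triggers it

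*Combined protocol and SAP*

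**What the plan says.** Four statements in section 10 matter.

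- **Section 10.1, Compression therapy**, lists the harms expected from the stockings: "Incorrect measured compression stockings can cause skin damage, which can result in lacerations, blisters and pressure sores or necrosis". It continues: "Nerve damage or deep vein thrombosis can also develop". It then rates the risk as very small, because experts fit the stockings individually and only low compression classes are used.
- **Section 10.3, individual participant**, discontinues anyone in whom a study-related risk occurs, giving as examples "skin or nerve damage/deep vein thrombosis caused by compression stockings" and MRI contraindications.
- **Section 10.3, whole study**, gives one trigger and then closes the list. Ending the study is required "if significant and unobserved serious adverse health effects, which have not been known or observed so far, occur. Otherwise, a termination of the entire study" (quotation cut here). In full, the closing sentence reads: "Otherwise, a termination of the entire study is not planned".
- **Section 10.4** rests the medical justification on previous experience, on which "the risk of occurrence of unwanted events is stratified as extremely low".

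Section 8.2 plans about 25 patients aged 6 to 70. Section 7.2 has each of them wear both stocking classes within eight weeks.

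**The concern.** The harms that the protocol regards as most serious are the ones that its whole-study rule leaves out. Because section 10.1 names them, they are known, and the rule responds only to what was not known.

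The study is justified on the premise that these harms are very rare. Cases arising during the trial are the evidence that would test that premise, yet the written rule does not respond to them. If several patients were harmed through a common cause, such as a shared fitting or manufacturing fault, the text would handle each as a separate discontinuation and would call for no study-level decision while stockings went on being issued. Children from age 6 may be among the participants.

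**Working it through.** The protocol gives no event rate, count, threshold or error probability for stopping, so there is no figure of its own to reproduce. The main check compares the wording.

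**Step 1: does a named harm meet the trigger?** The trigger needs an effect that is serious and was not known or observed before.

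| Harm | Named in 10.1 | Individual rule (10.3) | Whole-study rule (10.3) |
|---|---|---|---|
| Skin damage up to necrosis | Yes | Participant discontinued | Not triggered: already known |
| Nerve damage | Yes | Participant discontinued | Not triggered: already known |
| Deep vein thrombosis | Yes | Participant discontinued | Not triggered: already known |
| Serious harm of a new type | No | Participant discontinued if study-related | Triggered |

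The rule depends on the type of harm, not on how often it occurs. For the first three rows the result is the same at every count from 0 to 25.

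**Step 2: does anything else fill the gap?** The closing sentence of the whole-study rule offers no second trigger. The text available for review describes no safety committee, interim safety review or adverse-event reporting process. The monitoring mentioned in section 12.1 concerns the availability of source documents. The part of section 3 (Responsibilities) before 3.2 was not available, so this statement covers the visible text only.

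**Step 3: scale, under assumed rates.** Take n = 25 (section 8.2) and an assumed risk p per patient of a named serious harm, independent between patients.

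- P(at least 1) = 1 − (1 − p)^25
- P(at least 2) = 1 − (1 − p)^25 − 25p(1 − p)^24

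| Assumed p | Expected cases, 25p | P(at least 1) | P(at least 2) |
|---|---|---|---|
| 1% | 0.25 | 0.222 | 0.026 |
| 5% | 1.25 | 0.723 | 0.358 |
| 10% | 2.5 | 0.928 | 0.729 |

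For example, at 5%: 1 − 0.2774 − 0.3650 = 0.358. If the true risk were well above what the protocol presumes, more than one case would be quite possible, and the written rule would still require nothing at study level. These counts are illustrations, not proposed thresholds.

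**The case against.** The other side has a fair case.

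- **The scheme is coherent in two tiers.** An expected harm removes the participant, and an unexpected serious harm ends the study. This stands: the sections do not flatly contradict each other, and the known harms are managed at the level of the individual, with a low threshold. What is missing is any study-level treatment of known harms that accumulate. The closing sentence makes this more than silence, because it says that no other termination is planned.
- **The investigator could stop anyway.** This also stands. A reader might infer that the trial cannot be stopped however many known harms occur. The text does not say so: a stop that is not planned is not thereby prohibited. It simply has no criterion.
- **An unprecedented frequency or severity might count as unobserved.** This is possible only by stretching awkward wording. The rule speaks of effects not known or observed and sets no criterion of frequency or severity.
- **The rates are invented.** They are assumptions, and only 1% comes near the protocol's own view; there the chance of two or more cases is 2.6%. The binomial also treats patients as independent, so it does not describe a shared fault, where cases would cluster. It shows scale and nothing more.

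A reader might also infer that a second case of a new harm escapes the rule because the first has by then been observed. That has no practical force, since the first significant and serious new effect already requires termination.

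**Conclusion.** The point holds in a limited form. As written, the mandatory whole-study rule is not triggered by any number of cases of necrosis, nerve damage or deep vein thrombosis, and the visible text does not connect individual discontinuations to a decision about the study. This follows from the wording and needs no assumed rate.

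It does not show that the trial is unstoppable, that affected participants are left without protection, or that such events are likely. The chances of two or more cases (3%, 36% and 73% at 1%, 5% and 10%) depend on assumed, independent risks among 25 patients.

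The sponsor should correct this: it is a study-level safety gap, partly mitigated by the individual rule and cheap to close.

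**What to change.** Reconcile the compression risks in section 10.1, both parts of section 10.3 and the justification in section 10.4, by amending section 10.3. After the amendment, the whole-study criteria should no longer exclude by definition the serious harms named in section 10.1. The sponsor should also state how accumulating individual discontinuations for such harms bear on continuing the study. The content of that statement is for the sponsor; no threshold or clinical rule is proposed here.

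Merely striking the words that limit the rule to unknown effects would not be a neutral edit. The obligation to terminate would remain, so a single known serious event could be read as compelling the end of the study.

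The cost is a protocol wording amendment, with no extra patients or visits. The downside is that the study might be reviewed or interrupted where the present text would let it run on.
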